#### b. Inclusion and Exclusion Criteria

# CV Wizard – Clinical Decision Support Tool (Study Aim 1)

NOTE: Individual patients are not being enrolled for this clinic-randomized study. The goal of the study is to examine the uptake and impact of implementing CV Wizard into regular care processes. In this clinic-randomized trial, the intervention is provided at the clinic level and targets clinic processes that are part of routine patient care. CV Wizard will automatically identify patients age 40-75 years with either (a) reversible risk of cardiovascular disease (CVD) >10%, (b) diabetes  $+ \ge 1$  uncontrolled risk factor or high A1c, or (c) existing atherosclerotic cardiovascular disease (ASCVD)  $+ \ge 1$  uncontrolled risk

factor for CVD events. However, clinics can *manually* run the CV Wizard tool for any patient aged 18 and older.

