We will also examine overall rates of each of the impact outcomes (BMI in normal range, controlled blood pressure, controlled LDL, controlled HbA1c, and non-smoking status) pre/post tool use to assess any changes in patterns for patients in Arm 1 for whom the tool was used compared to those in Arm 1 for whom the tool was not used as well as to Arm 2 patients. The date the tool was first used for each patient will be assigned as the start of the post-period.

Extent of adoption of a CDS tool like CV Wizard directly impacts its population-level impact. To differentiate between the tool's population level impact versus impact when used, we will conduct intent to treat (ITT) analyses to compare all targeted patients at intervention versus control clinics. We will also conduct effect of treatment on the treated (ETOT; also called per protocol) analyses limited to intervention CHC patients for whom the CV Wizard tool was used (results viewed / printed out) at the index visit, compared to intervention clinic patients for whom it was not used, and separately, to control clinic patients. The ITT analyses test the hypotheses that targeted patients in intervention clinics will have significantly lower CVD risk scores and higher rates of CVD risk factor control, at visits in the year post-index visit period, compared to similar patients in control clinics. The ETOT analyses test the hypotheses that targeted patients in intervention clinics for whom the CV Wizard CDS tool results are viewed and / or printed will have significantly lower CVD risk scores and higher rates of CVD risk factor control, at visits in the year post-index visit period, compared to similar patients in control clinics, and compared to patients in intervention clinics for whom the tool alerted but was ignored at the index visit.

Analyses will be stratified by first-time and repeat patients to see if there is a difference in tool use as well as examine whether the time between visits effects tool use among repeat patients.

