### **Intent to Treat Analysis**

Differences in change in outcomes will assessed using multi-level mixed models. Intra-class correlation coefficients will be obtained at the patient, clinic, and CHC organization levels for each outcome showed that much organization-level variance could be attributed to the clinic level. Thus, clustering was accounted for by random effects for clinic and patient, and a fixed effect for organization. Analyses will adjust for fixed effects: distribution of eligible patients by age, race / ethnicity, gender, rural / urban status, and federal poverty level (FPL) at index visit; number of ambulatory visits during the follow-up period; and time from index to last visit. These variables were selected *a priori* and will be confirmed by descriptive analyses, to determine whether there are significant differences between baseline intervention and control organization and patient characteristics. After checking distributions, negative binomial mixed-models or poisson mixed-model will be used for reversible risk analyses, and linear-mixed models for all other outcomes.

Patients diagnosed with diabetes during the follow-up period will be excluded from reversible risk analyses because diabetes might be diagnosed more often with CDSS use. Presence of diabetes raises reversible risk estimations even if CVD risk factor control was addressed; this exclusion will remove the possibility of confounding based on likelihood on new diabetes diagnosis.

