#### **Effect of Treatment on the Treated Analysis**

Per-protocol analyses require adjusting for loss to follow-up and off-protocol therapies or treatments, but if group differences vary too greatly, model misspecification can yield biased estimates. Propensity score methods are an alternative. We will match intervention organization patients in three categories of tool use (never used during follow-up, used once, used more than once) to control organization patients. Counts of tool use will include use at index visit or subsequent study period visits, excluding the last visit. Matching variables will include age, FPL, outcome of interest at baseline, race / ethnicity, sex, count of ambulatory care visits post-index

visit, time from index visit to last study period visit, and clinic rural / urban status. Propensity scores will be estimated using nearest-neighbor matching with replacement.

As analyses in other settings indicated CV Wizard's potential for greater impact among patients with higher baseline risk, analyses of change in reversible risk will be stratified by baseline risk <10% or ≥10%. The assumption being that patients with lower baseline risk are less likely to improve. Additionally, we will run analyses by quartile of baseline reversible risk among patients for whom the tool was ever used during follow-up, matched to controls as described above. Analyses of change in reversible risk will include all patients meeting study inclusion / exclusion criteria; for other outcomes, analyses were restricted to patients with uncontrolled baseline risk. Linear mixed models will be used for all outcomes and checked for normality of residuals.

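### Among patients targeted at index, the <10% / ≥10% baseline-risk split in the ETOT analysis cannot by itself separate risk level from diabetes/ASCVD; separately, neither condition is a matching variable.

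*Combined protocol and SAP*

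**What the plan says.** **Targeting.** Section 5.b (Inclusion and Exclusion Criteria, Study Aim 1) states: "CV Wizard will automatically identify patients age 40-75 years with either (a) reversible risk of cardiovascular disease (CVD) >10%, (b) diabetes" with at least one uncontrolled factor or a high A1c, or (c) existing ASCVD with at least one uncontrolled factor. Clinics may also run the tool by hand for any adult.

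**Population.** Section 7.a, Quantitative Data, says the ITT analyses "compare all targeted patients at intervention versus control clinics". It words the ETOT hypotheses in terms of "targeted patients in intervention clinics for whom the CV Wizard CDS tool results are viewed and / or printed". The same section also gives an Aim 1 inclusion rule based only on visits and age 40-75, which does not repeat the targeting criterion.

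**Strata.** Section 7.a, Effect of Treatment on the Treated Analysis: "analyses of change in reversible risk will be stratified by baseline risk <10% or ≥10" per cent. The stated rationale is that lower-risk patients are expected to improve less. The plan adds an analysis by quartile of baseline reversible risk among patients for whom the tool was ever used, with matched controls.

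**Matching.** The same section: "Matching variables will include age, FPL, outcome of interest at baseline, race / ethnicity, sex, count of ambulatory care visits" after index, time from index to last visit, and clinic rural/urban status. Neither diabetes nor ASCVD is named.

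**Diabetes in the score.** The Intent to Treat section removes patients whose diabetes is diagnosed during follow-up, on the ground that "Presence of diabetes raises reversible risk estimations even if CVD risk factor control was addressed". Patients with diabetes at index stay in.

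**The concern.** The stratification is meant to show whether the tool works better in patients at higher baseline risk. Because the cut coincides with route (a), "reversible risk of cardiovascular disease (CVD) >10" per cent, falling below it also largely determines how a targeted patient came to be targeted. A weaker effect below 10% would look like confirmation of the plan's expectation, yet it could arise because everyone in that stratum has diabetes or ASCVD and many in the other stratum do not. The plan does not acknowledge this.

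A second and distinct issue concerns the comparison within each stratum. Tool use is not randomised, so the ETOT contrast depends on matching. Diabetes and ASCVD help decide whether the alert fires and plausibly bear on the course of reversible risk, but they are not among the eight listed matching variables. At stake is the secondary conclusion about who benefits from the tool.

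**Working it through.** The plan gives no sample size, effect or power for these strata, so there is no stated figure to reproduce.

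**1. Who can be below 10%?** A patient is targeted if (a) or (b) or (c) holds. Baseline risk below 10% means (a) fails, so a targeted patient must enter by (b) diabetes or (c) ASCVD. This holds whether baseline risk means reversible or total risk, because reversible risk is part of total risk and cannot exceed it. Listing risk values of 2, 5, 9.9, 10, 10.1 and 20% against diabetes, ASCVD and uncontrolled factor (each yes/no) gives 9 targeted combinations below 10%, none without diabetes or ASCVD. There are 19 at or above 10%, of which 4 have neither. The mismatch between >10% (targeting) and ≥10% (stratum) touches only patients at exactly 10%.

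**2. Does the result depend on the population?** Yes. Read the inclusion rule in Quantitative Data literally, with no targeting criterion. Let *t* be the share of patients targeted (15-25%, Section 8, Security Measures; applying it to the analysed age group is an assumption) and *L* the share of targeted patients below 10% (assumed 10-50%). Taking baseline risk as reversible, so that untargeted patients fall below the cut:

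untargeted share of the low stratum = (1 − t) / [(1 − t) + tL]

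- t = 0.15, L = 0.1: 0.85 / 0.865 = 0.983
- t = 0.25, L = 0.5: 0.75 / 0.875 = 0.857

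On that reading about 86-98% of the low stratum would be untargeted, and step 1 would not describe it.

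**3. How far can the strata differ for the wrong reason?** All effect sizes here are assumptions. Let the effect be *a* points with diabetes/ASCVD and *b* without, regardless of baseline risk, and let *q* be the share of the high stratum with either condition. The low stratum then shows *a*, the high stratum qa + (1 − q)b, and the apparent difference (high minus low) is (1 − q)(b − a).

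| q | a = 0.5, b = 1.5 | a = b = 1.0 | a = 1.5, b = 0.5 |
|---|---|---|---|
| 0.3 | 0.7 | 0 | −0.7 |
| 0.5 | 0.5 | 0 | −0.5 |
| 0.7 | 0.3 | 0 | −0.3 |
| 0.9 | 0.1 | 0 | −0.1 |

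If risk level truly adds 1.0 point and disease adds *c*, the apparent difference is 1.0 − (1 − q)c. For q from 0.3 to 0.7 it runs from 0.3 to 0.7 when c = +1 and from 1.7 to 1.3 when c = −1. The contrast can be inflated, hidden or left untouched.

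**4. What does the matching list do?** It balances users against controls within a stratum. Without index diabetes and ASCVD, a high-stratum user with diabetes can be paired with a control who has neither condition but the same score. In the low stratum a diabetes patient can be paired with an ASCVD patient. Matching on the baseline score limits this only in part, since equal scores can have different causes. Adding the two conditions would not alter the composition found in step 1, so the two issues need separate remedies.

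**The case against.** The strongest points on the other side, and what stands:

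- **The plan already looks beyond the 10% cut.** Quartiles of baseline reversible risk are planned, and any quartile wholly above 10% is not confined to diabetes/ASCVD patients. This stands. A reader might infer that the plan cannot show anything about baseline risk; that goes too far. The lowest quartile or quartiles may still share the composition problem, and the mix of conditions may vary across the rest.
- **The composition claim rests on a reading.** The visit-and-age rule, manual runs and the counting of tool use at later visits could all bring in patients without either condition. This stands, so a flat statement that 100% of the low stratum has diabetes or ASCVD is not supported. The targeted reading is still the better one: both sets of hypotheses use it, and Section 9 says data are extracted for target patients.
- **The diabetes sentence in the Intent to Treat section concerns new diagnoses.** This stands. Index diabetes is already in the baseline score, which is matched. The sentence shows that diabetes moves the score, not that users and controls will be unbalanced.
- **Table 6 leaves further comorbidities to be decided.** True for covariates generally, but the ETOT matching list does not take that up.
- **Each stratum's estimate answers its own question.** Correct; only the comparison between strata is ambiguous.

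**Conclusion.** The point holds in a limited form. If the ETOT population is patients targeted at index, the low stratum is essentially all diabetes or ASCVD while the high stratum is mixed, and a difference in effect between them cannot on its own be credited to baseline risk. The omission of both conditions from the matching list is a separate weakness of the within-stratum comparisons; it does not cause the between-stratum problem.

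The size is unknown. It depends on whether diabetes or ASCVD changes the effect and on their share in the high stratum, and the documents give neither. The 0.1 to 0.7 point range is an illustration under assumed inputs; the true distortion could be zero or of opposite sign. A reader might infer that the trial's main result is compromised. The documents do not support that: the primary Aim 1 comparison is Arm 1 versus Arm 2, and no stated figure changes. The case for acting is that the remedy is cheap and the ETOT comparison is non-randomised.

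**What to change.** In Section 7.a, Effect of Treatment on the Treated Analysis:

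1. Add index diabetes (yes/no) and index ASCVD (yes/no) to the matching variables.
2. State that the strata are formed among patients targeted at index (or, if a wider population is intended, say so), and whether baseline risk means reversible or total risk.
3. Report the <10% / ≥10% and quartile results also within patients who have diabetes or ASCVD, and show the mix of conditions in each stratum and quartile.
4. State that a difference between the pooled strata will not, by itself, be read as an effect of risk level.

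The cost is SAP wording and some extra output. Both conditions are already identified because they drive the alert. The downside is somewhat fewer close controls per patient; since matching is with replacement, some controls may be reused more often, with some loss of precision.

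### Effect modification by baseline risk is hypothesised, but no arm-by-baseline-risk interaction is planned in any sample, and the quartile analysis is confined to matched tool users

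*Combined protocol and SAP*

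**What the plan says.** All references are to the combined protocol and SAP.

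- **Section 7.a, Effect of Treatment on the Treated Analysis.** Citing experience in other settings, the plan expects more benefit at higher baseline risk. It then states that "analyses of change in reversible risk will be stratified by baseline risk <10% or ≥10" per cent. As a further analysis, "we will run analyses by quartile of baseline reversible risk among patients for whom the tool was ever used during follow-up"; these users are matched to control patients in the same way. The matched sample is built from tool use: "We will match intervention organization patients in three categories of tool use" (never, once, more than once). The matching variables include the outcome at baseline and two quantities known only after the index visit: visit count and time to last visit. The model is given as "Linear mixed models will be used for all outcomes and checked for normality of residuals".
- **Section 7.a, Intent to Treat Analysis.** Here "negative binomial mixed-models or poisson mixed-model will be used for reversible risk analyses", with "random effects for clinic and patient, and a fixed effect for organization" and a list of covariates. The section names no baseline-risk subgroup and no arm-by-baseline-risk term.
- **Section 7.a, Quantitative Data.** Risk is calculated at the index visit for each study subject, so the modifier is available in both arms. ITT compares all targeted patients between arms.
- **Section 7.a, Statistical Power.** The only interaction named for Aim 1 is group by time.

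**The concern.** The plan states a directional hypothesis about effect modification but does not specify an analysis that tests it.

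First, whether the tool was ever used is decided after the index visit, largely by clinicians. The Secondary Analyses section itself sets out to find which patient, encounter, provider and clinic characteristics go with use. A gradient across quartiles of users could therefore partly reflect who was chosen for use. Matching on the baseline outcome deals with dependence of use on measured baseline risk. It does not deal with unmeasured reasons for use.

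Second, separate results in two strata or four quartiles do not show whether the effects differ. A reader who sees significance in one stratum and not in another may take that as support for the hypothesis when the true effects are equal.

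At stake is a secondary claim, that the tool helps high-risk patients more. The primary comparison of arms is not at stake.

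**Working it through.** **1. The plan's own power figure.** The documents state numeric power only for the virtual-care supplement: 6,000 per group, difference 5.0, SD 9.1 at both times, correlation 0.2, two-sided alpha 0.05, power 100%.

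- SD of change = √(9.1² + 9.1² − 2 × 0.2 × 9.1 × 9.1) = 11.51.
- Power = 1.000, so the figure reproduces.

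Aim 1 power cannot be reproduced, because its SD, intraclass correlation (ICC) and power are not given.

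**2. Inputs for Aim 1.**

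- From the documents: 60 clinics with more than 35 high-risk patients each, and examined effects of 1.5, 2 and 3 points.
- Assumed: 30 clinics per arm, so 30 × 35 = 1,050 patients per arm as a floor; SD of change 11.51, borrowed from the supplement; share of patients in one stratum q = 0.25 to 0.5; ICC 0 to 0.05.

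**3. What separate stratum tests would show.** Suppose the true effect is the same in both strata (1,050 per arm, ICC 0). The stratum SE is 11.51 × √(2/(1,050f)), where f is the stratum's share. With stratum powers p₁ and p₂, the chance that exactly one stratum is significant is p₁(1 − p₂) + p₂(1 − p₁).

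| Common effect | q | p₁, p₂ | Exactly one significant |
|---|---|---|---|
| 1.5 | 0.5 | 0.560, 0.560 | 49% |
| 1.5 | 0.25 | 0.321, 0.734 | 58% |
| 2 | 0.5 | 0.804, 0.804 | 32% |
| 2 | 0.25 | 0.512, 0.932 | 49% |

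With no effect at all, four independent quartile tests at 0.05 give a 1 − 0.95⁴ = 18.5% chance of at least one false positive.

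**4. What an ITT interaction could detect.** For a two-stratum contrast with N patients per arm, SE = 11.51 × √(1 − ICC) × √(2/(Nq) + 2/(N(1 − q))). The modifier is measured on patients, so clinic intercepts cancel; this assumes that the contrast does not itself vary by clinic.

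- At N = 1,050, q = 0.5, ICC 0: 11.51 × √(2/525 + 2/525) = 1.005.
- At N = 1,050, q = 0.25, ICC 0: 11.51 × √(2/262.5 + 2/787.5) = 1.160.
- Over the full range of q and ICC, the SE is 0.98 to 1.16.

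| Difference between stratum effects | Power at 1,050 per arm |
|---|---|
| 1.5 points | 25% to 33% |
| 2 points | 41% to 53% |
| 3 points | 73% to 87% |

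The difference detectable with 80% power is 2.80 × SE, or 2.7 to 3.3 points. It would be 1.6 to 1.9 points at 3,000 per arm and 1.2 to 1.4 at 6,000 per arm. Both sizes are assumptions, since no expected Aim 1 patient total is given.

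**5. The 10% cut against the targeting rule.** Section 5.b targets patients by (a) reversible risk above 10%, (b) diabetes with an uncontrolled risk factor or high A1c, or (c) existing ASCVD with an uncontrolled risk factor. If baseline risk means reversible risk, targeted patients below 10% must have entered by (b) or (c). The low stratum would then be mostly patients with diabetes or ASCVD, and the split would mix risk level with eligibility route. The ETOT section does not say for the 10% split whether baseline risk is total or reversible.

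**The case against.** **The 10% split may not be limited to the matched sample.** A reader might infer that all baseline-risk analysis is confined to matched patients. The heading and the linear models favour that reading, since the ITT section uses count models for reversible risk. But the sentence on the split mentions neither matching nor tool use, and a later sentence in the same paragraph says that reversible-risk analyses take in all patients who meet the study criteria. An ITT reading is not excluded. This objection stands. What remains is that the sample is unstated and that no interaction is planned on either reading.

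**Baseline risk is already matched.** This also stands, and it narrows the concern to unmeasured reasons for use.

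**More patients do not make ITT more sensitive.** A reader might infer that the larger ITT sample answers the question better because its standard error is smaller. The two analyses estimate different things. Suppose uptake u is equal across quartiles and the tool has no effect in non-users. A gradient D among users becomes uD in ITT, while the standard error shrinks only by √u. The ITT z-value is then √u times that in users: 0.45 at u = 0.2 and 0.89 at u = 0.8 (both uptakes are assumed). The case for ITT is lower bias, not precision.

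**The randomised data do not settle the matter at no cost.** If uptake varies with baseline risk, the ITT interaction mixes uptake with effect when used. Power is low at the design minimum. The count models, with the usual log link, test interaction on a ratio scale. The ITT set for reversible risk also drops patients diagnosed with diabetes during follow-up and requires a later visit, so it is not fully protected by randomisation. All of this stands and belongs in the plan as caveats. None of it makes separate strata a test of effect modification.

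**Conclusion.** The concern holds in a limited form. The plan hypothesises effect modification by baseline risk and names no arm-by-baseline-risk interaction in any sample. Its quartile analysis rests on a subgroup selected after the index visit, and the sample for its 10% split is unstated. Reading separate strata as evidence would mislead often: 32% to 58% discordance under a common effect of 1.5 to 2 points, given 1,050 per arm, ICC 0 and the supplement's SD. An ITT interaction avoids selection on tool use, but at that size it has only about 25% to 53% power for differences of 1.5 to 2 points. It should be read as an estimate, not as a decisive test. It addresses population-level impact, not impact when used. The documents do not support the stronger claims that the matched sample is certainly the only one planned, or that the randomised sample can answer the question at no cost. The primary ITT result is unaffected, so this is a minor improvement.

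**What to change.** 1. In the Intent to Treat Analysis section, pre-specify an interaction of arm with continuous index-visit reversible risk. If the model is longitudinal, use arm by time by baseline risk, with the lower-order terms.
2. Report it as an estimate with a confidence interval. Give model-based absolute differences across baseline risk alongside the ratio-scale term.
3. Show the strata at 10% for display only, with confidence intervals. Note that targeting route (a) needs reversible risk above 10%, so the low stratum would be mostly patients with diabetes or ASCVD.
4. In the ETOT section, state which sample the 10% split covers and whether baseline risk there is total or reversible.
5. Keep the matched quartiles, labelled as non-randomised and exploratory.
6. State that the ITT interaction concerns population-level impact, mixes uptake with effect when used, and has limited power at the design minimum.

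The cost is a few sentences and some added modelling. No new data are needed, because index-visit risk is already calculated for each subject in both arms.
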